FEV1 Forced expiratory volume in 1 second

fT3 Free T3 fT4 Free T4

FVC Forced Vital Capacity

GGT Gamma-Glutamyl Transferase

HCT Hematocrit

HDL High-Density Lipoprotein

HHM Hand-Held Myometry

Hb Haemoglobin

ITT Intention-to-Treat

LDH Lactate Dehydrogenase

Ver.04 25Jun2020 Page 7 of 43

Sponsor: ITALFARMACO
Protocol: DSC/15/2357/53

LDL Low-Density Lipoprotein

LOCF Last Observation Carried Forward

LSmeans Least Square means

LVED left ventricular end-diastolic

LVEDD left ventricular end-diastolic internal dimension

LVEF left ventricular ejection fraction calculation

LVES left ventricular end-systolic

LVESD left ventricular end-systolic internal dimension

LVOT left ventricular outflow tract

LVS left ventricular septal wall thickness

MCH Mean corpuscolar hemoglobin

MCHC Mean corpuscolar hemoglobin concentration

MedDRA Medical Dictionary for Competent Activities

MFAF Muscle Fibers Area Fraction

MFM Motor Function Measurement

MMRM Mixed Model Repeated Measures

MMT manual muscle testing

MRI Magnetic Resonance Imaging

MRS Magnetic Resonance Spectroscopy

PDHD Protocol Deviation Handling Document

PEF Peak Expiratory Flow

PK Pharmacokinetic

PPS Per Protocol Set

PR Pulse Rate

PT Preferred Term

PW posterior wall

QT QT interval

QTcF QT interval, Fridericia's correction

RBC Red Blood Cells

SAE Serious Adverse Event

Ver.04 25Jun2020 Page 8 of 43

Sponsor: ITALFARMACO
Protocol: DSC/15/2357/53

SAP Statistical Analysis Plan

SD Standard Deviation

SE Standard Error

SF-36 Short Form 36

SOC System Organ Class

TEAE Treatment-Emergent Adverse Event

TFT Timed Function Test

TSH thyroid-stimulating hormone

WB Western blot

WBC White Blood Cell

WHO-DRL WHO-Drug Reference List

Sponsor: ITALFARMACO
Protocol: DSC/15/2357/53

1. INTRODUCTION

This document describes the statistical methods and outputs required for the Final analysis for the phase II clinical trial DSC/15/2357/53. Details of study conduct, and data collection can be found in the study protocol (version 5.0 amendment 4, dated June 17, 2020).

1.1. Changes from The Study Protocol

The following changes have been made to the statistical methodology planned in the study protocol:

- Total fibrosis (primary endpoint): the main analysis will be based on log-trasformed data.
 Sensitivity analyses will be performed on the original scale and also applying different multiple imputation approaches (both MAR and MNAR)
- MRI (key secondary endpoint): same analysis planned for the primary endpoint
- Other secondary endpoints: statistical analyses will be performed by means of Mixed Model for Repeated Measures instead of ANCOVA
- Total WB dystrophin 1 and Total WB dystrophin 2 will be analyzed
- Difference between biopsy sites at baseline will be evaluated for Total fibrosis, Total CSA and MFA%

2. STUDY OBJECTIVES AND ENDPOINTS

OBJECTIVES	VARIABLES	ENDPOINTS
Primary objective(s):	Primary variable(s):	Primary endpoint(s):
Establish the histological effects of givinostat versus placebo administered over 12 months.	Fibrosis (%) assessed through histological examination of muscle biopsies	Mean change in mean total fibrosis (%) comparing the histology of muscle biopsies before and after 12 months of treatment with givinostat versus placebo.
Secondary objective(s):	Secondary variable(s):	Secondary endpoint(s):
To establish the macroscopic muscle effects of givinostat versus placebo administered chronically over 12 months assessed by MRI/MRS.	MRS variables: Fat Fraction in the vastus lateralis Fat Fraction in the soleus	Mean change in fat fraction of vastus lateralis and soleus comparing Magnetic Resonance Spectroscopy (MRS) before and after 12 months of treatment with givinostat versus placebo.

OBJECTIVES	VARIABLES	ENDPOINTS
	MRI variables: Fat Fraction of the lower limb muscles (i.e. whole thigh, quadriceps, medial thigh, hamstrings, triceps surae and Pelvis Girdle) measured by Dixon technique	Mean change in fat fraction of lower limb muscles (i.e. whole thigh, quadriceps, medial thigh, hamstrings, triceps surae and Pelvis Girdle) comparing Magnetic Resonance Imaging (MRI) before and after 12 months of treatment with givinostat versus placebo.
	Cross-Sectional Area (CSA) and contractile CSA of lower limb muscles (i.e. whole thigh, quadriceps, medial Thigh, Hamstrings, Triceps surae muscles and Pelvis Girdle)	Mean change in CSA and contractile CSA of lower limb muscles comparing MRI before and after 12 months of treatment with givinostat versus placebo.
To establish the other histological effects of givinostat versus placebo administered over 12 months.	Other histological parameters: - SLIDE I 1- MFA (%) 2- Adipose tissue (%) 3- Other histological structure (%) 4- Number of fibers with centralized nuclei 5- Total number of fibers counted in slide I	Mean change in other histology parameters comparing the histology biopsies before and after 12 months of treatment with givinostat.
	- SLIDE II 1- Number of Regenerative fibers (MYH3) 2- Total number of fibers counted in slide II - SLIDE III 1- Cross-Sectional Area Type I fibers (CSAI) 2- Cross-Sectional Area Type II fibers (CSAI)	

OBJECTIVES	VARIABLES	ENDPOINTS
	 3- Total Cross-Sectional Area (CSAI and CSAII) 4- Total number of fibers counted in slide III 5- Fiber size variability - Dystrophin 1- Total WB Dystrophin 1 and Total WB Dystrophin 2 	
To establish the efficacy of givinostat versus placebo administered chronically over 12 months in slowing disease progression.	Motor Function Measurement (MFM): 1- Standing and transfers (D1) 2- Axial and proximal motor function (D2) 3- Distal motor function (D3) 4- Total score (Total mark)	Mean change in MFM before and after 12 months of treatment with givinostat versus placebo.
	Time Function Tests (TFT): 1- 4-Stair ascent duration 2- Rising from floor duration 3- 10-Metre Walk/Run test duration	Mean change in Time Function Tests (time to climb four standard steps, time to rise from floor and time to walk/run 10 m) before and after 12 months of treatment with givinostat versus placebo.
	Functional Tests:	
	1- Distance walked after 6 minutes (6MWT)	Mean change in 6MWT distance before and after 12 months of treatment with givinostat versus placebo.
	2- Patients with < 10% worsening in 6MWT	Number and proportion of patients with < 10% worsening in 6MWT at the end of study will be compared between treatment groups.

OBJECTIVES	VARIABLES	ENDPOINTS
	3- Patients who lose ambulation during the study (6MWT not done because patient unable to physically perform the test)	Number and proportion of patients who lose ambulation during the study will be compared between treatment groups.
	4- Patients who lose the ability to rise from floor (Rise From Floor grading = 0)	Number and proportion of patients who lose the ability to rise from floor (from baseline through end of study) will be compared between treatment groups.
	Muscle strength measured by Hand Held Myometry (HHM):	Mean change in muscle strength (right/left knee
	 Left knee extension measurements Right knee extension measurements Left elbow flexion measurements Right elbow flexion measurements 	extension and right/left elbow flexion) before and after 12 months of treatment with givinostat versus placebo.
To evaluate the impact of givinostat versus placebo administered chronically on quality of life and activities of daily living.	Quality of life test (SF-36): 1- Items 2- Domains: 1- Physical Functioning (PF) 2- Role-Physical (RP) 3- Bodily Pain (BP) 4- General Health (GH) 5- Vitality (VT) 6- Social Functioning (SF) 7- Role-Emotional (RE) 8- Mental Health (MH) 9- Total score	Mean changes in quality of life (SF-36) before and after 12 months of treatment with givinostat as compared to placebo.
	Adverse events	

ODUCCTIVES	VADIABLES	ENDROINTS
OBJECTIVES	VARIABLES	ENDPOINTS
To assess the safety and tolerability of givinostat versus placebo administered chronically.	Vital Signs: 1- Height 2- Weight 3- Body mass index (BMI) 4- Sitting blood pressure systolic 5- Sitting blood pressure diastolic 6- Heart rate 7- Temperature	Number and proportion of patients experiencing treatment-emergent adverse events (TEAEs) and serious adverse events (SAEs) from Baseline through end of study (EOS). Summary of type, incidence, and severity of TEAEs and SAEs (Baseline through EOS). Changes from baseline to end of study of vital signs.
	Laboratory tests: 1- Biochemistry 2- Hematology 3- Coagulation 4- Urinalysis	Changes from baseline to end of study of clinical laboratory tests.
	Physical examination	Changes from baseline to end of study of physical examination.
	Pulmonary function:	
	 Forced Vital Capacity (FVC) Forced Expiratory - Volume at 1 second (FEV1) FVC/FEV1 Peak Expiratory Flow (PEF) 	Changes from baseline to end of study of pulmonary function.
	Cardiac function parameters	

ODIFOTUES	MADIANIES	ENDROUNTS
OBJECTIVES	VARIABLES	ENDPOINTS
	1- ECG 2- ECHO	Changes from baseline to end of study of Cardiac function parameters.
To evaluate the pharmacokinetic (PK) profile of givinostat administered chronically in the target population	Details will be provided in a specific PK protocol.	Summary of the PK of givinostat and its major metabolites.
Secondary Exploratory objective(s):	Exploratory variable(s):	Exploratory endpoint(s):
To evaluate the correlation between the PK profile of givinostat and pharmacodynamics (PD) data.	Details will be provided in a specific Statistical Analysis Plan.	PK-PD correlation analyses between metrics of exposure and the efficacy/safety endpoints of givinostat.
To evaluate a possible disease-related biomarker - Genetic:	LTBP4 and osteopontin genotype	Analyses to explore whether the effects of givinostat versus placebo administered chronically may be related to the type of LTBP4 or osteopontin genotype.
- Serum	Serum Biomarkers. Details will be provided in a specific Statistical Analysis Plan.	Evaluation of serum circulating proteins as potential biomarkers for BMD.
To explore additional disease-related MRI biomarkers.	Details will be provided in a specific imaging protocol. Details will be provided in a specific Statistical Analysis Plan.	Additional evaluations of other muscle image parameters assessed by MRI.

Sponsor: ITALFARMACO
Protocol: DSC/15/2357/53

OBJECTIVES	VARIABLES	ENDPOINTS	
To evaluate the functional tests velocity of givinostat versus placebo.	Velocity for each functional test will be computed from the following variables: 1- 4-Stair ascent 2- Rising from floor 3- 10-Metre Walk/Run test	Mean change in Time Function Tests' velocities before and after 12 months of treatment with givinostat versus placebo.	

[figure not shown]
3. BACKGROUND AND RATIONALE

3.1. Overall Study Design and Plan Description

This is a phase 2, randomized, double-blind, placebo-controlled study. Ambulant patients who have provided written informed consent will undergo a 4-week screening period to determine eligibility for the study. Approximately 51 eligible patients will then be randomized in a 2:1 ratio to be treated with givinostat or placebo for a period of 12 months. The randomization process will be stratified by the factor related to the concomitant steroids use at baseline (yes vs. no). Patients who complete the study (i.e. 12 months of treatment) will be asked to return for a follow-up visit 4 weeks after the end of treatment.

An overview of the study is provided in Figur.

Figure 1: Study Design

Sponsor: ITALFARMACO
Protocol: DSC/15/2357/53

A total of 12 visits will take place during the study: Screening (V1, V2), Randomization (V3), Treatment (V4-V10), End of Study (V11) and Follow-up (V12). Visits during the treatment period will take place every 12 weeks except for the first 2 months, when they will occur every 2 weeks to allow close monitoring of hematological safety parameters. Patients may be evaluated more often if necessary, for safety reasons. Patients who discontinue the study treatment early will be asked to come in for an Early Withdrawal Visit within 4 weeks after the last dose of study treatment. Patients who have ongoing AEs at discontinuation will be followed until resolution or stabilization.

3.2. Selection of Study Population

The study will enroll adult male patients with an established genetic diagnosis of Becker Muscular Dystrophy. A complete list of all inclusion and exclusion criteria is provided in Sections 7.1 and 7.2 of the study protocol. Stopping rules and withdrawal reasons are described in Section 7.3.1 of the same protocol.

3.3. Treatment

3.3.1. Treatment Administered

Givinostat or placebo oral suspension (10 mg/mL) is administered twice daily (bid) (in a fed state) as indicated in the table below:

Weight (kg)	≥30 and <40	≥40 and <50	≥50 and <60	≥60 and < 70	≥70
Dose (mg) bid	26.7	33.3	36.7	40	46.7
Oral suspension (mL) bid	2.7	3.3	3.7	4.0	4.7

The dosage to be administered is based on patient weight because the weight significantly affects the givinostat clearance.

Additional information on "Dose Modifications" can be found in the study protocol section 8.2.2.

3.3.2. Method of Assigning Patients to Treatment Group

TREATMENT RANDOMIZATION

Approximately 51 eligible patients will be randomized in a 2:1 ratio to be treated with givinostat or placebo for a period of 12 months. The randomization process has been stratified by the concomitant steroids use at baseline (yes vs. no).

Sponsor: ITALFARMACO
Protocol: DSC/15/2357/53

BIOPSY SITES RANDOMIZATION

At Visit 1, after having filled in the "Eligibility criteria" eCRF page, eligible patients will be randomized to one of the two following sequences to assign to the patient:

V2: Right Arm - V11: Left ArmV2: Left Arm - V11: Right Arm

Randomization will be balanced in a ratio of 1:1 and will not be stratified.

PHARMACOKINETIC (PK) SAMPLING RANDOMIZATION

Blood samples for PK analysis of Givinostat and its metabolites should be collected at 4 visits: Visits 5 (Week 4), 8 (Week 12), 9 (Week 24) and 11 (Week 48).

All patients will have a total of 6 PK blood specimens drawn during the study:

- Two samples drawn pre-dose, these 2 specimens must be drawn at 2 different visits;
- One sample drawn between 0 and 2 hours post-dose;
- One sample drawn between 2 and 4 hours post-dose;
- One sample drawn between 4 and 6 hours post-dose;
- One sample drawn between 6 and 10 hours post-dose.

Eight sequences of combinations will be randomly selected from all the possible ones and each sequence of combinations will be randomly allocated to randomized patients in a ratio of 2:1 (Givinostat vs. Placebo).

PK randomization will be stratified according to the treatment group assigned at randomization.

3.3.3. Prior and Concomitant Therapy

A complete list of all prohibited medication or concomitant therapy requiring caution is provided in section 8.7.2 of the study protocol.

3.4. Schedule of Time and Events

The detailed Schedule of Assessments (SoA) is provided in sections 9 of the study protocol.

3.5. Sample Size and Power Estimation

The hypothesis to be tested in this study is as follows:

$$H_0: \mu_G - \mu_P = 0$$
 vs $H_1: \mu_G - \mu_P \neq 0$

where μ_G and μ_P the mean change from baseline to 12 months in total fibrosis (%) for the givinostat and placebo groups respectively.

The primary hypothesis to be tested in this study is that total fibrosis (%) will increase less in the givinostat group than in the placebo group so the primary efficacy variable of the study is the mean change from baseline to 12 months in total fibrosis (%).

Ver.04 25Jun2020

Sponsor: ITALFARMACO Protocol: DSC/15/2357/53

A sample size of 48 patients with evaluable baseline biopsies (in a 2:1 ratio, 32 and 16 respectively) will provide 80% power to test the null hypothesis of no treatment effect (givinostat – placebo) on total fibrosis vs the alternative hypothesis that the treatment effect is \geq 9% using a two-sided t-test with alpha level of 5% and assuming a common SD of 10% (with the SD being based upon blinded interim data from first 20 patients with valid biopsies).

Allowing for an approximate 5% of patients with not evaluable biopsies, the total number of patients to be randomized is 51 (i.e. 34 in givinostat arm and 17 in placebo arm).

After the first 20 baseline muscle biopsies was collected, an interim blinded sample size reassessment was undertaken to check the SD assumption used in sizing the trial. Details are capture in the specific SAP for the Interim Analysis.

After study enrollment was completed and baseline data were collected for all patients, a second blinded interim analysis was performed to obtain a preliminary overview of the baseline patient characteristics.

4. DEFINITIONS AND GENERAL METHODOLOGY

4.1. General Methodology

Continuous data will be summarized by mean, standard deviation (SD), median, first and third quartiles, minimum and maximum. Categorical data will be presented by absolute and relative frequencies (n and %) or contingency tables.

All statistical tables, listings, figures and analyses will be performed by means of SAS® release 9.4 or later (SAS Institute, Inc., Cary, NC, USA).

Two-sided alpha level 0.05 will be considered. No alpha level adjustment will be carried out for primary and secondary outcome variables.

4.2. Definitions

Definition of Screening Failures

Screening failures are defined as patients who consent to participate in the clinical trial but are not subsequently randomly assigned to the study treatments.

Definition of Baseline

For all evaluations, the last available assessment collected during the screening phase or before the first study treatment dose, is considered as baseline assessment, with the exception of 6 Minute Walking Test whereby, if more than one value is recorded for the baseline, the mean value will be taken.

First/Last Administration of Study Treatment

The date of first administration of study treatment is the earliest start date when study treatment was administered and recorded on the "IMP Dosage" eCRF page.

Sponsor: ITALFARMACO
Protocol: DSC/15/2357/53

The date of last administration of study treatment is the last end date when study treatment was administered and recorded on the "IMP Dosage" eCRF page.

Study day

Study day is defined as the number of days from the study reference date to the visit/event date.

It is calculated as:

Study day = Visit/event date - Reference date + 1 day

If the visit/event date is before the reference date, then the study day is calculated as follows: Study day = Visit/event date - Reference date

The reference day is used to calculate the "Study day" variable it is defined as the date of the first drug administration. If this date is missing or not done, then the reference date will be null, and the study day will be not calculated.

4.3. Coding of Therapies and Medical Terms

Medical history and Adverse Events will be coded using the last available version of MedDRA; prior and concomitant medications will be coded using the last available version of WHO Drug Dictionary.

4.4. Handling of Drop-Outs or Missing Data

4.4.1. Missing or Partial Dates

The following imputation rules will be applied in case of partially missing information:

- Day missing => day will be replaced with 15
- Day and month missing => day and month will be replaced with July 1st
- Day, month and year missing => no imputation will be done.

Additional imputation rules for partial dates:

Prior, concomitant and steroid medications

Start date

When only the start day is missing, the last day of the month is imputed. When both day and month are missing, January 1st will be imputed. If day, month and year are missing no imputation will be done but medication will be assumed to be started before first intake.

End date

When only the end day is missing, the last day of the month is imputed. When both day and month are missing, December 31st will be imputed.

Sponsor: ITALFARMACO
Protocol: DSC/15/2357/53

If day, month and year missing no imputation will be done and medication will be assumed as concomitant medications.

Diagnosis date

When only the day is missing, the first day of the month is imputed. When both day and month are missing, January 1st will be imputed.

No imputation will be done if day, month and year are missing.

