6.4.2. Concomitant medications

Prior (i.e. medications ended before first intake), concomitant (i.e. medications started before first intake and ongoing at the baseline) and steroid medications (used at baseline) will be presented as the number and percentages of patients with at least one prior/concomitant/steroid medication. Prior concomitant and steroid medication will be also classified using the WHO-DRL drug dictionary (using the most recent version) and summarized overall by WHO Anatomical Therapeutic Chemical /ATC) Class and Preferred Term.

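### A medication start date missing only its day is set to the end of that month, so a drug begun earlier in the first-dose month and still in use counts as neither prior nor concomitant under SAP 6.4.2

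*SAP*

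**What the plan says.** SAP 4.4.1 opens with a general rule for partial dates ("Day missing => day will be replaced with 15") and then gives separate rules for particular kinds of date. For prior, concomitant and steroid medications the start-date rules are:

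- Day missing: "When only the start day is missing, the last day of the month is imputed".
- Day and month missing: "When both day and month are missing, January 1st will be imputed".
- Whole date missing: "no imputation will be done but medication will be assumed to be started before first intake".

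The medication end-date rule is worded in the same way: "When only the end day is missing, the last day of the month is imputed". For the diagnosis date the direction is reversed: "When only the day is missing, the first day of the month is imputed". Nothing in the section limits an imputed start to the recorded end date or relates it to the date of first dose.

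SAP 6.4.2 defines concomitant medications as "medications started before first intake and ongoing at the baseline", and prior medications as those that stopped before first dose. The planned output is patient counts and percentages, summarised by ATC class and Preferred Term. Protocol 8.7.2 and 13.5 define concomitant differently, as any treatment taken after study drug has been given.

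**The concern.** Three start-date rules for the same variable point in two directions. When the month is unknown, or the whole date is unknown, the drug is placed as early as possible or simply taken to precede first dose. When the month is known, so that more is recorded, the drug is placed as late as possible. A record with less information is kept as a baseline drug, while a better one can be lost. The match with the end-date wording suggests a drafting slip.

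At stake is the description of what patients were taking when study treatment began. Protocol 8.7.2 asks for dates of use on every medication and names several classes that need caution, so these tables give context for the platelet, QTcF and triglyceride summaries.

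**Working it through.** The plan states no figure on this point, so there is none to reproduce. The check applies the rule to every possible day.

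**Inputs.** The imputation rules come from SAP 4.4.1 and the classification tests from SAP 6.4.2. Month length L is 28, 30 or 31 days. All day combinations are weighted equally, which is my assumption.

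**Step 1: drug in use at baseline, begun before first dose in the same month.** Let the true start be day S and first dose day D, with S < D. There are L(L−1)/2 such pairs.

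- Last-day rule: the imputed start is L, and L ≥ D always. No record passes the test of starting before first dose, so 100% fail. When first dose falls on the last day (L−1 pairs) the two dates are equal, and the test still fails. The imputed start is strictly later than first dose in a share 1 − 2/L.
- Day-15 rule: fails when D ≤ 15, which covers 0 + 1 + … + 14 = 105 pairs.
- First-day rule: fails only if D = 1, which is impossible when S < D.

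Because the drug had not stopped before first dose, it is not prior either.

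**Step 2: complete end date E in the same month as the partial start, S ≤ E.** There are L(L+1)/2 pairs. Under the last-day rule the start falls after the end unless E = L, a share of 1 − 2/(L+1). Under day 15 it does so when E ≤ 14, which is 1 + 2 + … + 14 = 105 pairs. Under the first-day rule it never does. If both days are missing, both become the last day and there is no inversion.

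**Step 3: the opposite error under a first-day rule.** For drugs truly started on or after first dose in that month (S ≥ D), the imputed start precedes first dose unless D = 1, a share of 1 − 2/(L+1).

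| | L = 28 | L = 30 | L = 31 |
|---|---|---|---|
| Baseline drug fails start test, last day | 100% | 100% | 100% |
| of which strictly after first dose | 92.9% | 93.3% | 93.5% |
| Baseline drug fails, day 15 | 105/378 = 27.8% | 105/435 = 24.1% | 105/465 = 22.6% |
| Baseline drug fails, first day | 0% | 0% | 0% |
| Start after end, last day | 93.1% | 93.5% | 93.8% |
| Start after end, day 15 | 105/406 = 25.9% | 105/465 = 22.6% | 105/496 = 21.2% |
| Start after end, first day | 0% | 0% | 0% |
| Later drug counted as pre-dose, first day | 93.1% | 93.5% | 93.8% |

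**Examples.** First dose 20 March, drug begun in March on an unknown day and ongoing: the imputed start is 31 March, so the drug is neither prior nor concomitant. Start in March on an unknown day, end 10 March: the derived start of 31 March is after the end. If first dose was after 10 March, this course is still prior, because that status uses the end date alone.

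**The case against.** The case for leaving the rule alone has several parts.

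- **Inverted intervals.** A reader might infer that the medication tables would show impossible intervals. SAP 6.4.2 plans only counts by class and term, with no durations. Protocol 13 says in general that collected data will be listed, but not that derived dates would appear. The inversion stays a flaw in the derived data. A short course finished before first dose keeps its prior status.
- **Particular drug classes.** A reader might infer that the cautioned classes would go missing systematically. Protocol 7.1 requires six months without significant change for corticosteroids, ACE inhibitors and alpha or beta blockers, some of which are on the P-glycoprotein list in Appendix 16.3. Protocol 7.2 requires six months of stable treatment and controlled levels for patients enrolled with hypertriglyceridemia. Lipid treatment begun on study under Protocol 8.8 starts after first dose, so SAP 6.4.2 excludes it whatever date is imputed.
- **The steroid factor.** A reader might infer an effect on the primary model. The stratification value is entered in the IWRS at randomization (Protocol 8.3), and nothing indicates that it is derived from imputed dates.
- **The definition does more damage than the date rule.** Under the protocol's definition an ongoing drug stays concomitant whatever start is imputed. Under SAP 6.4.2 any drug started on or after first dose is in neither category, even with a complete date. This stands, and the fix has to cover it.
- **A possible rescue.** SAP 4.4.1 also treats a medication whose end date is wholly missing as concomitant. If an ongoing drug's empty end date is read that way, the drug is kept. But the clause concerns missing dates, does not waive the start test in SAP 6.4.2, and would not help a drug in use at baseline that later has a recorded stop date.
- **Accuracy in the other direction.** The last-day rule correctly dates as post-dose the drugs that truly began after first dose. A start that recent may also be less likely to lack its day, though that is inference.

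**Conclusion.** The point holds as a minor one. Applied with SAP 6.4.2 as written, the last-day rule misclassifies every drug in use at baseline whose day-less start lies before first dose in the month of first dose. Starts in earlier months are classified correctly, as are drugs truly begun on or after first dose so far as the start test goes. The documents do not give the number of partial dates; a few records is a reasonable expectation, not a figure from the plan. Start-after-end inversions need a complete end date in the start month before its last day, and they do not change who counts as prior. Primary efficacy is not affected.

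The conclusion assumes that the medication rules override the general day-15 rule, that SAP 6.4.2 governs the tables, and that the fallback for a wholly missing end date is not meant for ongoing drugs. The percentages also assume equally likely days; the 100% and 0% results for the start test do not depend on that.

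**What to change.** In SAP 4.4.1:

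- For a medication start missing only its day, impute the first of the month, unless other recorded information shows that the start was on or after first dose.
- Never impute a start later than the recorded end date. This cap alone is not enough, because a capped start can still fall on or after first dose.
- Keep the last-day rule for end dates only, and say whether an ongoing drug counts as having a missing end date.

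In SAP 6.4.2, reconcile the definition of concomitant with Protocol 8.7.2 and 13.5, so that drugs started on or after first dose have a category.

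The edit is a few lines of SAP text and the matching derivation code. The statistical cost is the one in Step 3: where nothing else is recorded, about 93–94% of day combinations for drugs truly started on or after first dose in that month would count as started before it. That is the direction the SAP already takes for less complete start dates.
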